[figure not shown]
Effect of T6 Dermatome Electrical Stimulation on Gastric Motor Functions, Appetite, Satiation, Satiety and Weight Loss in Individuals with Overweight and Class I Obesity

NCT# NCT03261531

4/18/2017

Background

Previous studies demonstrated that upper abdominal dermatome electrical stimulation inhibited postprandial antral motility, possibly through activation of somatovisceral stimulation or central mechanisms. Electrical stimulation of the dorsal columns of the spinal cord to prevent the perception of intractable neuropathic pain signals was associated with appetite reduction and weight loss; percutaneous electrical neurostimulation of dermatome T6 was associated with appetite reduction and, along with a proper diet, achieved a significantly greater weight reduction than diet alone in morbidly obese subjects. The effects of T6 dermatomal electrical stimulation on gastric motor functions and body weight in otherwise healthy overweight or class I obese volunteers are unclear.

Hypothesis

T6 dermatomal electrical stimulation results in delay of gastric emptying of solids, reduction in gastric volume, inhibition of appetite, and weight loss in healthy volunteers who are overweight or have class I obesity.

Aim

In participants with BMI 25-34.99kg/m², treated before and after two meals of the day with T6 dermatomal electrical stimulation (delivered by a TENS unit), we aim to compare baseline measurements of gastric emptying of solids, fasting and postprandial gastric volume, satiation, satiety, appetite, and body weight with measurements after three months of treatment.

Methods

We shall perform scintigraphic testing of gastric emptying of solids, as well as tests of satiation, satiety, gastric volume, appetite assessment, plasma ghrelin (total), GLP1 and PYY in 16 healthy overweight or class I obese volunteers receiving T6 dermatomal electrical stimulation.

Significance

This study will form the foundation for the potential subsequent application of dermatome electrical stimulation for treatment of overweight and/or class I obesity.

[figure not shown]
Research Plan

BACKGROUND

An implantable gastric stimulator (gastric pacemaker) has been used to treat obesity; this achieves excess weight loss up to 40% in approximately 1 year. The stimulator can be placed laparoscopically or endoscopically, but is invasive (1-3). The modulation of neuronal activities and release of certain hormones with an implantable gastric stimulator may explain the reduction of appetite and the increase of satiety, such as a decrease in ghrelin levels (4).

[figure not shown]
Viscerovisceral spinal sympathetic reflexes appear to play an important role in the autonomic control of thoracoabdominal viscera, such as the heart and great vessels (5). However, somatic stimulation may also affect visceral function through autonomic reflexes. The best known somatovisceral response is the effect of cold pain on vasomotor reactions (6). Evidence suggests that the gastrointestinal tract may also be influenced by such somatovisceral reflexes; thus, in anesthetized rats, cutaneous stimuli applied to the abdomen and hind paw decrease and increase stomach motility, respectively. Whereas the latter reflex response appears to relay centrally and the efferent limb of the reflex is located in vagal fibers, the response to abdominal stimulation involves a somatosympathetic reflex that relays at the level of the spinal cord, being retained in cervical cord-transected rats (7).

In studies performed by the Principal Investigator 30 years ago (8), sustained somatic stimulation by transcutaneous electrical nerve stimulation (TENS) was applied to the skin of human volunteers while simultaneously monitoring their upper gastrointestinal phasic pressure activity, extraintestinal vasomotor indices, and plasma levels of putative humoral mediators of autonomic reflexes (Figure 1). Figure 1.

Stimuli were applied either to the hand (C8-T1) or to the upper abdomen (T5-T10) to determine whether impulses at these two dermatomes produced different effects on fed antral phasic pressure activity. TENS resulted in significant reduction (p=0.007) in antral motility index when applied to the hand and abdomen, as compared with sham stimulation (Figure 2). This was associated with increases in skin conductance and plasma beta-endorphin levels, but there were no changes in pulse, blood pressure, or circulating catecholamine levels. No qualitative changes in proximal intestinal pressure activity were detected. These studies suggested that sustained somatic stimuli resulted in reduced postprandial antral phasic pressure activity and the similarity in the responses to TENS applied to the hand and abdominal dermatomes suggests that the somatovisceral responses may relay at the central level.

Figure 2.

While effects of TENS dermatomal stimulation on gastric emptying was not evaluated in the earlier studies, more recent data suggested that cutaneous gastric electrical stimulation slowed gastric emptying (9). Furthermore, Electrical stimulation of the dorsal columns of the spinal cord to prevent the perception of intractable neuropathic pain signals in two patients was associated with appetite reduction and weight loss (10). In a large study, Ruiz-Tovar et al. showed that percutaneous electrical neurostimulation of dermatome T6 was associated with appetite reduction than diet alone in morbidly obese patients (11).

Figure 3 shows effects on pre-treatment and post-treatment appetite scores and proportion with weight loss >5kg (11).

[figure not shown]
Figure 3.

[figure not shown]
T6 stim active Diet alone

T6 stim active Diet alone

Proportion with weight loss >5kg

Appetite score (0-10 VAS)

The effects of T6 dermatomal electrical stimulation on gastric motor functions in otherwise healthy overweight or class I obese volunteers are unclear.

HYPOTHESIS AND SPECIFIC AIM

Hypothesis

T6 dermatomal electrical stimulation results in delay of gastric emptying of solids, reduction in gastric volume, inhibition of appetite, and weight loss in healthy volunteers who are overweight or have class I obesity.

Aim

In 16 participants with BMI 25-34.99 kg/m², treated before and after two meals of the day with T6 dermatomal electrical stimulation (delivered by a TENS unit), we aim to compare baseline measurements of gastric emptying of solids with measurements on day 1 of treatment and after 4 weeks and 3 months of treatment. We also aim to compare baseline measurements of fasting and postprandial gastric volume, satiation, satiety, appetite, and weight with measurements after three months of treatment.

EXPERIMENTAL DESIGN

Overweight or class I obesity participants who are not on metformin and have not been diagnosed with type 2 diabetes mellitus (other than dietary advice for borderline hyperglycemia) will be recruited for the study.

Participants will undergo baseline measurements of height, weight, BMI, pulse, blood pressure, gastric function, satiation, satiety, and incretin hormones, over a period of 3 to 7 days. In an open-label study, all 16 participants will receive 15-minute T6 dermatome cutaneous stimulations with a TENS unit applied immediately before ingestion of two of the main meals of the day (breakfast and evening meal), and 60-minute stimulations applied immediately after ingestion of these meals.

[figure not shown]
Participants will attend the Mayo Clinic Clinical Research Trials Unit during the first day of treatment, within 2 weeks from completion of baseline testing. During this visit (day 1 of treatment), devices will be provided and participants will receive training on self-administering electrical stimulation. Hence, the first set of electrical stimulations will take place at Mayo Clinic. On this day, participants will also undergo a gastric emptying test as a measure of the acute effect of T6 dermatome cutaneous stimulation on gastric emptying.

Participants will apply the stimulus four times daily for a treatment period of at least 3 months, at the time of breakfast and evening meals (starting 15 minutes preprandially and immediately postprandially for 60 minutes). After 4 weeks of treatment, the participants will be asked to return to the Clinical Research and Trials Unit for a repeat of the gastric emptying study identical to the procedure performed at baseline. During the three-month treatment period, participants will keep a diary of weight, measured on the same weighing scales in their homes once weekly, and a weekly appetite record (0-10cm VAS, paper diary). The stimulation parameters will be: 200 µsec pulse width at 20 Hz with a goal amplitude range of 18-20 mA. Each stimulation will begin at 0 mA and increase quickly to achieve the 18-20 mA dose. Clinical trial stimulation will be limited to an accumulated maximum of 150 Joules each day; For example, two 15-minute and two 60-minute stimulation sessions at 200 µsec pulse width, 20 Hz and 25 mA deliver an accumulated 40.5 Joules per day. Participants that do not tolerate the discomfort or develop nausea likely caused by the TENS unit, will report to the investigational team thepost-prandial duration of stimulation may be reduced from the targeted duration of 60 minutes postprandially).

During the final week of the three-month treatment period or at the time of early withdrawal, participants will undergo the same measurements as performed during the previous gastric emptying test days. During these studies, participants will receive 15-minute T6 dermatome cutaneous stimulations with the TENS unit immediately before meal ingestion and 60-minute stimulations immediately after meal ingestion, in the different tests.

Figure 4 is a schematic that summarizes the main events that will take place in this study.

Figure 4.

METHODS

Participants

Overweight or class I obese participants who are not on metformin and have not been diagnosed with type 2 diabetes mellitus (other than dietary advice for borderline hyperglycemia) will be recruited for the study. The objective is to have 16 participants complete all investigative testing over approximately 14 weeks. Therefore, we may screen and enroll up to 36 participants in order to ensure 16 fulfill eligibility criteria and complete the study.

Inclusion Criteria

- a. Overweight and obese adults (BMI ≥25 kg/m² and ≤34.99 kg/m²) residing within 125 miles of Mayo Clinic in Rochester, MN; these will be otherwise healthy individuals with no unstable psychiatric disease and not currently on treatment for cardiac, pulmonary, gastrointestinal, hepatic, renal, hematological, neurological, or endocrine (other than hyperglycemia on diet) disorders.
- b. Age: 18-65 years
- c. Gender: Men or women. Women of childbearing potential will be using an effective form of contraception, and have negative pregnancy tests within 48 hours of enrollment and before each radiation exposure.
- d. Subjects must have the ability to provide informed consent before any trial-related activities.

Eligible individuals will be asked to avoid taking additional medications and supplements for the duration of the study, unless reviewed and approved by the study team.

Exclusion Criteria

a. Abdominal surgery other than appendectomy, Caesarian section or tubal ligation

- b. Positive history of chronic gastrointestinal diseases, systemic disease that could affect gastrointestinal motility, or use of medications that may alter gastrointestinal motility, appetite or absorption, e.g., Orlistat
- c. Positive history of diabetes mellitus or use of hypoglycemic medications
- d. Positive history of spinal cord injury and/or chronic back pain
- e. Significant untreated psychiatric dysfunction based upon screening with the Hospital Anxiety and Depression Inventory (HAD) (12), a self-administered alcoholism screening test (AUDIT-C) (13), and the Questionnaire on Eating and Weight Patterns (binge eating disorders and bulimia) (14). If such a dysfunction is identified by a HAD score >11 or difficulties with substance or eating disorders, the participant will be excluded and given a referral letter to his/her primary care doctor for further appraisal and follow-up.
- f. Intake of medication, whether prescribed or over the counter (except multivitamins), within 7 days of the study. Exceptions are birth control pill, estrogen replacement therapy, thyroxine replacement therapy, low dose analgesia or anti-inflammatory medications (Acetaminophen and Ibuprofen) and any medication administered for co-morbidities as long as they do not alter gastrointestinal motility including gastric emptying and gastric accommodation.
- g. Subjects may also be excluded from participation for other factors at the discretion of the principal investigator.

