Yes, very much	Would you like to eat something sweet?	No, not at all	average of the four individual scores (satiety + fullness + 100-prospective food consumption + 100-hunger / 4.	
Yes, very much	Would you like to eat something salty?	No, not at all	6. Plasma gastrointestinal hormones (ghrelin, GLP-1 and PYY) by radioimmunoassay measured	
Yes, very much Yes, very much	Would you like to eat something savoury?	No, not at all	at fasting, and 15, 45, and 90 minutes	
	Would you like to eat something fatty?	No. not at all		

postprandially during the NDT. The primary endpoint is the peak postprandial level. CCK levels will not be measured in the current study, since they were non-informative in our prior studies. Total ghrelin will be measured by a radioimmunoassay technique (Linco Research, Inc., St. Charles, MO). The assay uses ¹²⁵I-labeled ghrelin and a ghrelin antiserum to determine the level of total ghrelin in plasma.GLP-1 will be measured as the biologically active GLP-1 (active and total) using a 2-site non-competitive immunoassay based on enzyme-labeled quantification of GLP-1 detected by a fluorogenic substrate. PYY will be measured by radioimmunoassay (Linco Research, Inc., St. Charles, MO). PYY exists in at least 2 molecular forms, 1-36 and 3-36, both of which are physiologically active and are detected by the assay.

7. Self-administered questionnaires assessing affect, exercise performance, attitudes, satisfaction with body image, and eating behavior (12-14,23-26).

Statistical Analysis

Sample size assessment - Sample size assessment is based on the results of primary endpoints in the Mayo Clinic lab. Assuming the intra-individual coefficient of variation (or standard deviation) is similar to the inter-individual variation, we have used the SD_{inter} for estimating the power of the study (n=16, baseline versus post-treatment).

Response	Mean	SD	Predicted detectable effect size (%(absolute #)), n=16 on treatment compared to baseline, paired analysis
Gastric emptying, T _{1/2} min*	121.7	29.8	18.4% (22.4 min)
Fasting gastric volume, ml**	225	65	21.8% (49mL)
Gastric accommodation, ml**	507	100	14.7% (75mL)

Data obtained from *ref. 16 and **ref. 20; predicted detectable effect size is shown with 80% power, α =0.05.

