The sample size of 16 on-treatment relative to baseline will have sufficient power to detect a difference in gastric emptying of 22.4 min, of fasting gastric volume of 49mL, and in gastric accommodation of 75mL.

Statistical Methods

It is anticipated that all primary and secondary endpoints will be normally distributed. We shall use a paired student's t-test to compare study parameters (differences between baseline and on-treatment). An analysis of covariance may be examined using gender and BMI as covariates, since these may significantly affect gastric functions such as satiation, maximum tolerated volume, and gastric emptying.

Interim Analysis

An administrative interim analysis will be completed after 6 subjects have completed at least 4 weeks of treatment. The data will be submitted in a blinded fashion to the study sponsor's statistician while the investigative team remains blinded to the treatments. This interim analysis will be conducted for administrative purposes to provide information about future planning of other research activities. The

conduct of this study will not be altered and all planned research activities will proceed until the completion of the targeted 16 subjects.

Primary endpoints

- 1. Body weight change from baseline
- 2. Gastric emptying $T_{1/2}$ after day 1 treatment
- 3. Gastric emptying $T_{1/2}$ after 3 months treatment

Secondary endpoints

- 1. Fasting gastric volume
- 2. Postprandial gastric volume or accommodation volume
- 3. Gastric emptying % at 1 hour in day 1 and end of three months of treatment
- 4. Satiation: volume to fullness (grade 3) and maximum tolerated volume (grade 5)
- 5. Satiety: kcal intake at buffet meal
- 6. Appetite score during satiety meal test and at weekly intervals (at home)
- 7. Plasma ghrelin, GLP-1 and PYY fasting
- 8. Peak postprandial plasma ghrelin, GLP-1 and PYY fasting

Anticipated Results and Significance

We anticipate greater weight loss with active treatment with dermatomal stimulation compared to baseline. The sample size is not sufficient to appraise twice versus once daily treatment. However, the data will be tabulated for descriptive analysis. The physiological measurements will provide information about the potential mechanisms involved in any beneficial effects on weight and appetite.

Potential Pitfalls, Precautions Taken, and Alternative Strategies

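### The weekly home appetite score (part of secondary endpoint 6) has no specified pre-treatment entry to serve as baseline for the planned paired comparison

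*Combined protocol and SAP*

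**What the plan says.** - **When the home record is kept.** Experimental Design: "During the three-month treatment period, participants will keep a diary of weight, measured on the same weighing scales in their homes once weekly". The sentence goes on to add "a weekly appetite record (0-10cm VAS, paper diary". The question, the end anchors and the direction of this scale are not given, and neither is the day of the first entry.
- **What is measured at baseline.** Experimental Design: "Participants will undergo baseline measurements of height, weight, BMI, pulse, blood pressure, gastric function, satiation, satiety, and incretin hormones, over a period of 3 to" (the upper limit of the range is one week). No home appetite record is on that list. Weight is, so the home weight diary has a clinic baseline beside it.
- **The gap before treatment.** Participants attend the research unit "during the first day of treatment, within 2 weeks from completion of baseline testing". No diary entry on appetite is described for this interval.
- **The endpoint.** Secondary endpoint 6 reads "Appetite score during satiety meal test and at weekly intervals (at home"). It joins a laboratory score and a home score on one line.
- **The comparison.** Hypothesis and Specific Aim: "We also aim to compare baseline measurements of fasting and postprandial gastric volume, satiation, satiety, appetite, and weight with measurements after three months of treatment". Statistical Methods gives a paired t-test to "compare study parameters (differences between baseline and on-treatment"). An analysis of covariance with gender and BMI is mentioned as optional. No trend analysis or change from week 1 is specified.
- **The laboratory score.** Quantitative Traits, item 5, defines it as the average of four 100 mm ratings, "satiety + fullness + 100-prospective food consumption + 100-hunger / 4", taken every 30 minutes between a liquid breakfast and the buffet meal.

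**The concern.** Inhibition of appetite is part of the trial's hypothesis. The Background motivates it with a T6 stimulation study shown as appetite before and after treatment on a 0-10 scale. The home diary uses the same numerical range, so it is the measure here that most resembles that evidence, yet only its on-treatment half is specified.

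A single-arm trial has no reference other than each participant's own pre-treatment value. If no such value is collected, the natural substitute is the first diary entry, which may already be an on-treatment value. Whatever the treatment did before that entry then disappears from the estimate. Someone following the protocol to the letter could complete all 16 participants and find that the planned paired difference cannot be formed for this component, with no way to recover the missing value afterwards.

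**Working it through.** **1. The plan's own figures.** The sample-size table gives no figure for appetite. Its three detectable differences reproduce with a two-sided paired t-test, n = 16, alpha 0.05, 80% power, and the SD of the difference set to the tabulated SD. The standardised detectable difference is 0.7495 SD, so:

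| Response | SD | 0.7495 x SD | Stated |
|---|---|---|---|
| Gastric emptying half-time | 29.8 min | 22.3 min | 22.4 min |
| Fasting gastric volume | 65 mL | 48.7 mL | 49 mL |
| Gastric accommodation | 100 mL | 74.9 mL | 75 mL |

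The table is sound for these responses and does not bear on this point.

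**2. Specified pairs for the home score.** A paired difference needs one pre-treatment and one on-treatment value per participant. The text specifies weekly on-treatment values and no pre-treatment value. The number of pairs it guarantees is 0 of 16.

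**3. Exposure before the first entry.** Experimental Design sets four sessions a day.
- First entry on day 1 before stimulation: 0 sessions.
- First entry at the end of week 1: 7 x 4 = 28 sessions.

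The wording allows anything in this range.

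**4. Effect on the estimate.** Let D be the true change from before treatment to month 3, and f the fraction of D already present at the first entry. Change measured from that entry is D x (1 - f). The documents give no value for f, so a range is shown as an assumption:

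| f | Share of D recovered |
|---|---|
| 0 | 100% |
| 0.25 | 75% |
| 0.5 | 50% |
| 1 | 0% |

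For any f between 0 and 1 the error is toward no effect.

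**5. Can the laboratory score stand in as baseline?** No. It is a mean of four 100 mm items around a test meal, whereas the home record is a 0-10 cm scale in daily life. Subtracting one from the other has no meaning, and the protocol does not propose it.

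**6. Direction of the laboratory score.** Satiety and fullness enter positively; hunger and prospective consumption enter as 100 minus the rating. Assume each line is scored from its left anchor to its right. Suppose (illustration) hunger and prospective consumption fall from 70 to 40 while satiety and fullness rise from 30 to 60:
- before: (30 + 30 + 30 + 30) / 4 = 30
- after: (60 + 60 + 60 + 60) / 4 = 60

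The laboratory appetite score doubles as appetite falls. The direction of the home scale cannot be worked out, because its question and anchors are not given.

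**The case against.** **The first entry may precede stimulation.** Day 1 is a supervised clinic visit, and an entry made there before the first session fits the wording. The schematic of study events (Figure 4) is not available either, so an entry shown there cannot be excluded. This stands. A reader might infer that the home score certainly lacks a pre-treatment value and that the comparison is impossible. The documents support only that no text requires such a value.

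**The appetite aim does not depend on the diary.** The laboratory score belongs to the satiety test, which is measured at baseline and again at the end of treatment, and buffet intake is a separate secondary endpoint. This also stands. It would be wrong to conclude that the appetite hypothesis cannot be examined.

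**The two scores are not shown to run in opposite directions.** A reader might infer that endpoint 6 combines two scores of opposite sign. Only the laboratory direction can be read from the text, and nothing in the plan pools the two. What remains is that the home item is undefined and that the shared label invites misreading.

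**Nothing shows that appetite changes early.** The day 1 test concerns gastric emptying alone. It is not evidence on the speed of any appetite effect, so f in the working is unknown and could be near 0.

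**A lead-in entry would not be a clean baseline.** Diet education is given at enrollment (Recommended Diet), so an entry after it may reflect the diet. This is a fair point about the remedy, and the fix takes it into account.

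**Weekly entries can still be described as a trend.** True, but that is not the planned comparison, and no such analysis is specified.

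**Conclusion.** The concern holds for the home component of secondary endpoint 6, on the text available. The plan names the endpoint and a baseline comparison but does not require the baseline to be collected. From 0 to 28 sessions may come before the first entry. If part of a lasting effect appears in that time, change from the first entry understates it by that part, from nothing to all of it. The conclusion assumes that the unseen schematic adds no pre-stimulation entry and that the first diary entry would be used in place of a baseline.

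The practical weight is moderate. This is one of two components of one of eight listed secondary endpoints, in an open-label study that calls itself a hypothesis-generating pilot. It still merits correction, because the missing value cannot be recovered later and costs almost nothing to collect.

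**What to change.** 1. Issue the same 0-10 cm scale at the first baseline visit and require at least one entry before the first stimulation on day 1. Ideally, take one entry before the diet education and one after it, so that the effect of the diet can be seen separately. If the education comes before the first baseline visit, the earlier entry has to be taken at enrollment, before the dietitian session.
2. In Statistical Methods, name the last pre-stimulation entry, or the mean of the post-education entries, as baseline for the paired analysis of the home score.
3. State the question, the anchors and the direction of the home scale. Note beside endpoint 6 that the laboratory composite rises as appetite falls, and report the two components separately with their directions.
4. If pre-stimulation entries cannot be added, say that the home score is descriptive or analysed as a within-treatment trend.

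**Cost.** One or two more diary entries per participant, and a few lines of text. The lead-in runs from about 3 days (the shortest baseline period) to about 3 weeks (7 days of baseline testing plus 14 days to day 1). No visit is added: participants already attend for baseline tests, meet a dietitian at enrollment and keep a daily food diary.

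### The withdrawal-time assessment stands in for month 3, and no month-3 weight is planned after stimulation stops, although weight change is primary endpoint 1

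*Combined protocol and SAP*

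**What the plan says.** All references are to the combined protocol and SAP.

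- **Final assessment (Experimental Design).** "During the final week of the three-month treatment period or at the time of early withdrawal, participants will undergo the same measurements". The content is then defined as "as performed during the previous gastric emptying test days"; weight is not named there.
- **Weight during the study (Experimental Design).** "During the three-month treatment period, participants will keep a diary of weight, measured on the same weighing scales in their homes once weekly". The text does not say what happens to this diary if stimulation stops.
- **Time point (Hypothesis and Specific Aim).** Baseline is compared for "satiation, satiety, appetite, and weight with measurements after three months of treatment".
- **Endpoint (Primary endpoints).** The first item reads "Body weight change from baseline", with no time point.
- **Enrolment (Methods, Participants).** "we may screen and enroll up to 36 participants in order to ensure 16 fulfill eligibility criteria and complete the study".
- **Analysis (Statistical Methods).** A paired t-test of baseline against on-treatment values. No analysis set, missing-data rule or rule for using a withdrawal-time weight is given.
- **Purpose (Potential Pitfalls, item b).** The study is a hypothesis-generating pilot, meant among other things to characterise the variation in weight loss for sizing a later trial.

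**The concern.** The month-3 visit and the withdrawal visit are alternatives, and no contact after withdrawal is described. Stopping the device while staying in the study is not described either. If the protocol is followed as written, someone who withdraws early has a final assessment at that moment and no planned weight at month 3.

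Stopping is unlikely to be random. The protocol itself expects discomfort and nausea in some participants, and people who see no benefit may also give up. Month-3 weights would then come mainly from those who tolerated the device. Two results are exposed: the mean weight change, which is primary endpoint 1, and its variation, which the pilot is meant to pass on to the next trial. This is a matter of collection before it is a matter of analysis, because no later choice of analysis set can recover a weight that was never taken.

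**Working it through.** **1. The plan's own figures.** The Statistical Analysis table gives detectable differences for n = 16, 80% power and α = 0.05. With a two-sided paired t-test (15 degrees of freedom) and the SD of the difference set to the tabulated SD, the detectable difference is 0.749 SD.

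| Response | SD | 0.749 × SD | Stated |
|---|---|---|---|
| Gastric emptying T½ | 29.8 min | 22.3 min | 22.4 min |
| Fasting gastric volume | 65 mL | 48.7 mL | 49 mL |
| Gastric accommodation | 100 mL | 74.9 mL | 75 mL |

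The figures reproduce. There is no row for body weight, so the plan offers no weight SD or expected loss to work from.

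**2. Is it a power problem?** The number to treat for 16 completers is 16/(1 − d) for dropout d. The plan gives no d. For assumed values of 10%, 20%, 30% and 40% the result, rounded up, is 18, 20, 23 and 27. All lie within the ceiling of 36 before screen failures are counted. Enrolling to 16 completers protects the sample size, so what remains is who those 16 represent.

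**3. Where could a month-3 weight come from after an early stop?**

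| Source | Planned at month 3 after an early stop? |
|---|---|
| Final assessment | No; it is held at withdrawal instead, and weight is not named in its content |
| Weekly home diary | Not stated; it is tied to the treatment period |
| Any later visit | None described |

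**4. Shift in the mean (illustration).** Let p be the share of treated participants who stop, C the completers' mean loss, and δ the amount by which the stoppers' month-3 loss falls short of C. The all-treated mean is (1 − p)C + p(C − δ) = C − pδ, so completers overstate it by pδ. With p = 0.25 and δ = 2 to 3 kg, both assumed:

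- 0.25 × 2 = 0.5 kg
- 0.25 × 3 = 0.75 kg

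**5. Shift in the variance (illustration).** If both groups have the same SD σ, the all-treated variance is σ² + p(1 − p)δ². The added term is 0.25 × 0.75 × 4 = 0.75 kg² for δ = 2, and 0.25 × 0.75 × 9 = 1.69 kg² for δ = 3. With σ assumed to be 2 to 4 kg:

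- smallest: 0.75/16 = about 5% more than the completer variance
- largest: 1.69/4 = about 42% more

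For a fixed target difference, the next trial's sample size scales with this variance.

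**The case against.** A reader might infer that withdrawal ends weight collection, or that anyone who stops stimulation never gives a month-3 weight. The documents do not say so. The home diary is separate from the final test visit, and the text is silent on it after stimulation stops. Early withdrawal is not defined, so equating it with stopping the device is an inference. The study schematic (Figure 4) is not shown in the available text and might add detail.

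Other limits also stand:

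- Withdrawal is not the only response to intolerance. Experimental Design allows the post-meal session to be shortened, and the T6 Dermatomal Stimulation section lets the principal investigator decrease any parameter. Stopping may therefore be infrequent.
- A reader might take 36 − 16 = 20 as the number who could lack a month-3 weight. That difference includes screen failures, who are never treated. That those who stop are replaced is likewise inferred from the enrolment plan.
- The 0.5 to 0.75 kg is the product of assumed inputs. If stoppers lost as much as completers, the shift would be zero.
- That weight would still be falling at an early exit is plausible on the recommended diet, but the documents give no weight trajectory.
- The planned comparison is on-treatment. Making off-device weight the sole primary value would change the question asked.
- This is a single-arm, open-label pilot, so there is no between-arm contrast to bias.

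These points limit the wording and the size. They do not remove the gap, since silence on collection can leave the weight missing just as an explicit stop would. Pilot status does not excuse it either, because retention and the variation in weight loss are among the things the pilot is meant to establish.

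**Conclusion.** The concern holds in a limited form. The protocol substitutes a withdrawal-time assessment for the month-3 assessment and does not provide for a month-3 weight after stimulation stops, although the Aim compares weight at three months and weight change is primary endpoint 1. With enrolment aimed at 16 completers, the mean loss and its variation may not describe everyone treated.

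The effect on endpoint 1 cannot be computed from the documents. The illustrative shift in the mean, and the 5% to 42% range for the variance, rest wholly on an assumed stopping share, an assumed shortfall in loss and, for the variance, an assumed SD common to both groups. The change is worth making because it is cheap and the missing weight cannot be recovered afterwards.

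**What to change.** **Experimental Design**

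- Define stopping stimulation separately from leaving the study.
- Ask those who stop stimulation to continue the weekly home weight and to give one weight at month 3.
- Record the date and reason for stopping.
- Keep the withdrawal-time tests as written.

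**Primary endpoints and Statistical Methods**

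- Set the time point of endpoint 1 at month 3, and state whether the clinic or the home scale supplies the weight.
- Keep the on-treatment paired comparison.
- Report beside it the month-3 change in all treated participants, using the month-3 weight whether or not the person was still on the device. Do not substitute the withdrawal-time weight for it. State how many have no month-3 weight.

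**Cost.** A protocol amendment, a consent line and one extra weight for each person who stops, with no added radiation. The mean loss in all treated participants may turn out smaller. In a single-arm study the off-device weights are descriptive and do not serve as a diet-only control.
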